According to the various interventions stated above, the outcomes of relevance are readmissions (8-12,15,17,22,24-26,28-44), mortality (7,8,10,12,25,27,28,30-32,38-41,44), length of stay (LOS) (12,25,28,29,32,38,41,45), direct discharge from the ED (12,29), time at home (10,25,27,34), duration of readmission (10,25,34) and physical functional status (8,25,27,28,30,31,34,40,43-45). A successful intervention may be reflected in a shorter LOS, lower risk of readmissions, longer time at home, maintained functional status and a shorter duration of readmission. We suggest that a significant and effective intervention under the best circumstances is reflected in these outcomes. Readmissions are usually considered as such, when the admission occurs within 4 hours after and before 30 days after discharge. Among the frail, in-hospital and post-discharge mortality is high, needing frequent assessment. As shown by Pedersen et al. (7), mortality differs with regard to type of dwelling. Former studies have shown a significant and remarkable reduction of LOS (reduction from median 3 days to median 2 days) and an increase from 49 % to 56 % of patients discharged directly from the ED due to the possibility of early follow up by a geriatric team (12). Functional status is of relevance, especially combined with mortality data, since a better survival of the frailest may be combined with a worsened functional status in the total group. Patient Related Outcome Measures (PROMs) will be assessed and added as secondary outcomes during the project. Patient satisfaction and costs are other relevant outcome measures with regards to the triple aim principle, but will not be included in the present Ph.D. project.

Conclusion

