All frail patients admitted to the ED and the Department of Geriatrics are randomized 1:1 to one of two different follow-up efforts prior to CGA performed during hospitalization. Thereby the intervention is randomly split into two groups:

- An intervention (I) consisting of CGA during hospitalization and early post-discharge follow-up care by a community nurse and a GP
- An intervention (II) consisting of CGA during hospitalization and early post-discharge follow-up care, including continued CGA and tailored follow-up care, by a geriatric team

The intervention cohort will be compared to a control cohort consisting of similar frail elderly who receive usual care without involvement of geriatric care during hospitalization and after discharge.

Hypotheses

- The geriatric team follow-up is as effective as a community nurse and GP follow-up measured by readmission, mortality, LOS, direct discharge from ED and physical functional recovery
- The effects of three transitional follow-up approaches (community nurse and GP; multidisciplinary geriatric team; usual care) are similar measured in terms of readmission, time at home, duration of readmission, LOS, direct discharge from ED, mortality and PROMs
- When stratified into subgroups with regards to level of frailty (moderate and severe) and type of dwelling, the geriatric team follow up is as good as community nurse and GP follow-up measured by readmission, mortality, LOS, direct discharge from ED and physical functional recovery

Methods

Design

The first study is conducted as a randomized controlled trial (RCT) using two different degrees of intervention. The second study is a cohort study where the two groups in the RCT are compared to an unexposed control group. The third study is sub-group analyses of the RCT data according to frailty status and type of dwelling.

Study population

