The patients in the control group are discharged to usual care and do not receive early follow-up visits. Usual care features municipality services and optionally a GP home visit (see Appendix 2). Eligible control patients are consecutively included by a Research Assistant. The estimated level of frailty will be assessed by the PhD-student based on a MPI-screening tool fitted to be performed using only medical record data. This fitted tool will be tested and validated prior to the inclusion of the control group. Clinicians will be blinded to the result of the MPI-screening of the control subjects to ensure that discharge is performed in accordance with usual care.

Outcomes

The primary outcome is readmission within 30 days after discharge. Secondary outcomes are:

- Mortality 30 days after discharge and 90 days after admission
- Length of stay during primary admission and total length of stay including following readmissions
- Direct discharge from the Emergency Department
- Time at home before readmission
- Duration of readmission
- Physical functional status 30 days after discharge (Functional Recovery Score)
- Patient Related Outcome Measures as defined by a focus group of included patients and/or their relatives

Statistical analyses

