Data are registered in REDCap and exported to STATA version 15 for the statistical analyses. Statistical significant results are defined as a p-value of 5% or less. The two intervention groups and the control group will be compared with regard to baseline measures. If needed, statistical corrections for demographical differences and level of frailty will be made. The use of services and other contents of follow-up will be assessed and compared if possible. Baseline data collected for the entire study population before discharge are: age, gender, date of admission, co-habitation status, number of drugs, and level of frailty measured by MPI including functional status by means of Functional Recovery Score (FRS) at discharge. Follow-up data for the control group will be collected on type of planned care after discharge. Follow-up data for the entire study population will be collected on: department of discharge, date of discharge, primary diagnosis at discharge, dwelling after discharge, readmission date, and death date. For the intervention cohort additional data are collected: date of follow-up, provided services after discharge, number and date of visits (team, GP, nurse) after discharge, phone-calls to the geriatric team or GP, nutritionist consultations, FRS after 30 days, date of dispatch of discharge summary. Additional data will be collected by review of the electronic patient records.

Outcomes

A hazard ratio (HR) for readmissions will be calculated using a Cox regression model with death as a 'competing risk' factor. The HRs of readmission with 95% confidence intervals (95% CI) for interventions I and II will be compared individually and to the control group. The interventions will be tested in subgroup analyzes based on: patients discharged directly from the ED, type of dwelling and level of frailty. Median LOS, time at home before readmission and duration of readmission will be calculated and compared using the Wilcoxon rank-sum test. The mortality hazard ratio will be calculated also using the Cox regression model. The change in functional status at discharge and 30 days after discharge will be compared in a linear regression model. Data will be analyzed in accordance with intention-to-treat and per-protocol analysis.

Sample size

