Power analysis is based on a pilot study performed from June to December 2017 using the method stated above, and earlier studies by Pedersen et al.(7,12), where patients selected by diagnoses associated with readmission were randomized to early geriatric follow-up visits or usual care. Readmissions were reduced from 23% to 12%. Data collected during the pilot study showed 13.7% readmissions in the Intervention group I compared to 8% readmissions in the Intervention group II. Based on the pilot study data, allowing a 5% drop-out rate and a 30-day mortality rate of 10%, the number of patients in each trial arm should be 758 in order to achieve a power of 90% and a level of significance of 5%. Data collected during the same pilot study showed a 90-day mortality rate of 20.6% in Intervention group I compared to 15.6 % in Intervention group II. To achieve a power of 80% and a level of significance of 5% with regards to mortality, the sample size of each arm should be 1,019, including a 5% drop-out rate.

Perspectives

This study may uncover a need for specialized and early efforts to support transfer of the frail elderly. We may find that some of the frail elderly are poorly supported by the present follow-up procedures, suggesting that comprehensive geriatric assessment and early follow-up intervention by a community nurse and a geriatric team should gain further currency in the future. This study may contribute to dimension health care services in the future. We hope to clarify the possible need for geriatric services outside university hospitals. The results are directly transferable to Danish regional hospitals and may be of importance in other Western countries.

Ethics

The study has been approved as a quality development project by the Regional Research Ethics Committee, Central Denmark Region (journal no. 197/2017), thereby no patient consent form is needed, and further referral to the committee not required. No patient will receive less than usual care, no extra treatment or examination will be applied, and no patient will be exposed to any additional risk because of the project. Participants may decline parts of or the entire intervention, including usual care, at any time. The project, which is a part of the national rate adjustment pool-project "Early post-discharge follow-up of the frail elderly – a intersectoral effort" in the Central Denmark Region, is approved by the Danish Data Protection Agency (journal no. 2012-58-006).

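### Time at home before readmission and duration of readmission are compared by rank-sum with no stated analysis set; taken as named, the test covers only readmitted patients, a set selected by the primary outcome

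*Protocol*

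**What the plan says.** The Outcomes section of the Protocol lists "Time at home before readmission" and duration of readmission as secondary outcomes and defines neither. The only analysis given for them, under Statistical analyses, is: "Median LOS, time at home before readmission and duration of readmission will be calculated and compared using the Wilcoxon rank-sum test". The Combined protocol and SAP has the same text.

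Three other places bear on the point:

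- Death is dealt with only in the readmission model: "A hazard ratio (HR) for readmissions will be calculated using a Cox regression model with death as a" competing-risk factor.
- A related outcome that can be computed for everyone is already planned: "Length of stay during primary admission and total length of stay including following readmissions".
- Outcome measures counts as signs of success "lower risk of readmissions, longer time at home, maintained functional status and a shorter duration of readmission". Of the three hypotheses, only the second, the three-approach comparison, names these two outcomes; it states that the effects "are similar measured in terms of readmission, time at home, duration of readmission, LOS, direct discharge from ED, mortality and PROMs". The Combined protocol and SAP words it the same way, without PROMs.

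Neither document gives an analysis set, a follow-up window, a censoring rule, or a value for patients who are not readmitted or who die first.

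**The concern.** A patient who is never readmitted has no readmission to time and no readmission stay to measure. If the two outcomes are analysed as named, patients enter the test only after having the primary event. An intervention that prevents readmissions changes who is in that set, so the readmitted patients in I and II need not be comparable even though the arms were randomised.

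The question answered also changes. The test shows whether the remaining readmissions come earlier or last longer. It does not show whether patients spend more days at home or fewer days back in hospital, which is how the plan describes success. A null result could be taken as support for the similarity hypothesis when readmissions have fallen. Longer remaining stays could be reported as harm when total readmission days have fallen.

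**Working it through.** **Inputs.** The Sample size section states: "Data collected during the pilot study showed 13.7% readmissions in the Intervention group I compared to 8% readmissions in the Intervention group II". It also gives 758 per arm (90% power, 5% drop-out, 10% 30-day mortality) and 1,019 per arm (80% power on 90-day mortality of 20.6% vs 15.6%, 5% drop-out). Allocation is 1:1. A 30-day window is assumed from the primary outcome. Tests are taken as two-sided at 5%.

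**1. The plan's own sizes reproduce.** With d = 0.137 − 0.08 = 0.057 and mean rate 0.1085:

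n = [1.960·√(2 × 0.1085 × 0.8915) + 1.282·√(0.137 × 0.863 + 0.08 × 0.92)]² / 0.057² = 624.

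The continuity correction, (n/4)·[1 + √(1 + 4/(n·d))]², gives 659, and 659 × 1.15 = 757.85, i.e. 758. For mortality the same method gives 970, and 970 × 1.05 = 1,018.5, i.e. 1,019.

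**2. Patients with a value.** Share readmitted = (13.7% + 8%)/2 = 10.85%.

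| Patients counted per arm | I (× 0.137) | II (× 0.08) |
|---|---|---|
| 758 × 0.95 × 0.90 = 648 | 89 | 52 |
| 758 × 0.95 = 720 | 99 | 58 |
| 758 | 104 | 61 |
| 1,019 × 0.95 = 968 | 133 | 77 |
| 1,019 | 140 | 82 |

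The 648 row is at the low end because it removes all deaths, although a patient who dies after a readmission still contributes a value.

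**3. Time at home, readmitted only.** 648 per arm, true cut 13.7% to 8%, 3,000 simulated trials per setting. Assumption: 40% of arm I readmissions fall in week 1 (the Readmission section says more than 40%), with times uniform within days 0–7 and 7–30. Of the 13.7 points in arm I, 5.48 then fall in week 1, and 5.7 points are prevented in all. If 20% of the benefit falls in week 1, arm II keeps 5.48 − 1.14 = 4.34 of its 8 points there (54%). At 40% it keeps 3.20 (40%, as in arm I), and at 60% it keeps 2.06 (26%).

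| Share of benefit in week 1 | II called worse | II called better |
|---|---|---|
| 20% | 28.0% | 0.1% |
| 30% | 11.3% | 0.4% |
| 40% (proportional) | 2.5% | 2.6% |
| 50% | 0.2% | 10.2% |
| 60% | 0.1% | 28.3% |
| 70% | 0% | 55.9% |
| 80% | 0% | 82.4% |

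Readmissions are 5.7/13.7 = 42% fewer in every row. With 720 per arm the 20%, 40% and 60% rows become 31.2/0.1, 2.6/2.9 and 0/31.4.

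A second model with constant hazards and no deaths gives medians among the readmitted of 14.4 vs 14.7 days. The readmitted-only test rejects in about 5% of trials; a rank-sum over all patients with time capped at 30 days rejects in about 91%.

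**4. Duration, readmitted only.** Assumed lognormal stays with median 3 days and log-SD 0.8: mean 4.13 days, 1.75 among stays below the median and 6.51 above it. Arm I bed-days per patient = 0.137 × 4.13 = 0.566.

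- If 20% of prevented stays are below the median, days saved = 0.057 × (0.2 × 1.75 + 0.8 × 6.51) = 0.317 (−56%). Arm II is called shorter in 57% of trials.
- If 50% are, it is called shorter in 2.5% and longer in 2.5%.
- If 80% are, days saved = 0.057 × (0.8 × 1.75 + 0.2 × 6.51) = 0.154 (−27%). Arm II is called longer in 57%, although its patients spend fewer days readmitted.

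Stays with median 6 and log-SD 1.1 give nearly the same rejection rates, with bed-days falling by 23–60%.

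**5. The other reading.** If never-readmitted patients are entered as 30 days at home and 0 days of readmission, fewer than half of each arm have any other value, so the medians are 30 and 0 in both arms. The time-at-home test favours arm II in 91–96% of trials, much as a test of the readmission rate would. Unless deaths have their own rule, a patient who dies at home on day 3 also scores 30.

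**6. All-patient measures.** 720 per arm, equal 10% mortality, 1,500 trials per setting. Readmission bed-days (Welch test) favour arm II in 61–93% and arm I in 0%. Rank-sum on days alive and out of hospital favours arm II in 59–65% and arm I in at most 0.1%. With no readmission difference but assumed mortality of 12% vs 8%, the second measure is significant in 39–41% while bed-days stay near 5%.

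**The case against.** The strongest reply is that the documents never restrict the test to readmitted patients, and they promise an intention-to-treat analysis. A reader might infer that the plan prescribes a comparison of 89 with 52 patients. It does not: that set follows from the outcome names and from a rank-sum test with no censoring or imputation rule. The intention-to-treat sentence does not settle the matter either, because it gives no value to a patient without a readmission.

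A reader might also infer that the test is tilted against the geriatric team. The documents do not support that. Arm II looks worse on time at home only if prevention falls disproportionately after week 1. With team follow-up planned for at most 7 days, extension allowed, early prevention is the more plausible pattern, and there the test favours arm II. The 20–80% splits of prevented stays have no basis in the documents; they show a range. Rejection in 5% under proportional prevention is correct behaviour for a test of timing among the readmitted. The fault lies in what the result would be taken to mean.

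Three limits stand:

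- The two outcomes appear only in the hypothesis behind the cohort study. It includes I versus II, but its contrasts with control were never randomised. No control number is given, so no firm count can be offered for them.
- The readmission model uses all patients, and total length of stay partly covers hospital use.
- An all-patient measure restricted to those discharged alive is itself defined after randomisation, which takes place on the day of admission and is open.

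**Conclusion.** The concern holds as a gap with a consequence. The analysis set and the values for never-readmitted patients and deaths are not stated. The natural reading gives a comparison selected by the primary outcome in about 11% of the randomised patients (89–140 vs 52–82). For the same 42% reduction in readmissions, that comparison can be null or favour either arm. The alternative reading is largely redundant with the readmission rate rather than misleading.

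The counts rest on the pilot rates and a 30-day window; a longer window would raise them. The rejection rates rest on assumed timing and stay distributions that the documents do not settle. It would go too far to infer that the trial's readmission result is compromised: the primary analysis does not use these two outcomes and would normally still show a benefit. The change should be made before analysis because the plan treats both outcomes as signs of success and their p-values could be reported as separate evidence.

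**What to change.** 1. Report median time at home before readmission and median duration of readmission among readmitted patients as description, without a p-value, and state that set.
2. Make the between-group comparison on readmission bed-days to day 30 after index discharge (0 if not readmitted), over all patients discharged alive, as a mean difference with a bootstrap confidence interval.
3. If a time-at-home comparison is kept, define it for all those patients, with the values for never-readmitted patients and deaths fixed in advance. Days alive and out of hospital is one option. Report it next to mortality, with mean days split into hospital days and days lost to death. The split matters: in simulations with fewer readmissions but mortality of 8% in I and 12% in II, the rank-sum favoured arm II in 5–7% and went against it in about 1%, while the mean difference went significantly against arm II in 13–29%.
4. State the number of in-hospital deaths per arm, because being discharged alive is determined after randomisation.

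The cost is SAP wording, changed definitions for two secondary outcomes and some programming. Readmission and death dates are already listed for the whole study population. The discharge date of the readmission is not listed; it would have to come from the planned record review, and duration of readmission needs it in any case. Two downsides remain: bed-days overlap with total length of stay, and a death-inclusive measure mixes in mortality.

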The population allocated to intervention comprises geriatric patients acutely admitted to the ED, Aarhus University Hospital (AUH) or transferred to one of the two geriatric wards at AUH. Subjects are included immediately on the day of admission at the ED, AUH and the Department of Geriatrics (wards 1 and 2), AUH, as shown in Fig. 1. Patients admitted to the ED at night and promptly discharged before enrollment to the intervention cohort can be performed the following day are not included. Likewise, patients to the control group are included immediately on the day of admission at the ED, Randers Regional Hospital (RRH), and at the medical wards 1, 2, 3 and 4, RRH. Patients transferred to other departments are excluded. Patients can only be included once. Enrollment and randomization to the intervention group are performed by therapists working in the ED or the geriatric wards. Enrollment to the control group is done by a Research Assistant. In the control group frailty screening is done by the PhD-student using a frailty screening tool based exclusively on data collected through medical records. The frailty screening tool will be validated by crosschecks performed by a blinded project Research Assistant. The results of the validation study will be analyzed and published during 2019.

Inclusion criteria:

- Aged 75 years or older
- Living within the municipality of Aarhus (except for the control group, see below)
- MPI-score = 2 (moderate frailty) or MPI score = 3 (severe frailty)

Exclusion criteria:

- Included in any other kind of follow-up schemes
- Declared terminally ill or undergoing palliative care at admission
- Admitted from one specific temporary nursing home with geriatric medical assistance (Vikærgården)
- Discharge or transfer to another department, including hospice
- MPI-score = 1 (low frailty)
- Discharged to one specific temporary nursing home with geriatric medical assistance (Vikærgården)
- The patient does not want a visit after discharge

Inclusion- and exclusion criteria to the control group are the same as for the two intervention groups, except that subjects eligible for the control group are living within the four municipalities of RRH: Randers, Favrskov, Norddjurs and Syddjurs.

Randomization

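### Against the Randers cohort, no covariate-adjusted method is named for length of stay, time at home or duration of readmission, so the promised correction has no stated vehicle for these outcomes

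*Protocol*

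**What the plan says.** The Design section of the Protocol describes three studies. The first is the randomised comparison of interventions I and II. Of the second it says: "The second study is a cohort study where the two groups in the RCT are compared to an unexposed control group". The controls are not randomised and come from elsewhere: "subjects eligible for the control group are living within the four municipalities of RRH".

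The second hypothesis is that the three approaches, ending with usual care, do not differ: "usual care) are similar measured in terms of readmission, time at home, duration of readmission, LOS, direct discharge from ED, mortality and PROMs". LOS is also a listed secondary outcome, in two forms: "Length of stay during primary admission and total length of stay including following readmissions".

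Under Statistical analyses, the three groups are to be compared at baseline, followed by "If needed, statistical corrections for demographical differences and level of frailty will be made". No trigger, model or covariate list is given. The Outcomes paragraph then names the methods:

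- Readmission: "A hazard ratio (HR) for readmissions will be calculated using a Cox regression model with death as a 'competing risk' factor". Mortality also has a Cox model, and functional change has a linear regression.
- LOS, time at home and duration of readmission: "Median LOS, time at home before readmission and duration of readmission will be calculated and compared using the Wilcoxon rank-sum test".

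The Combined protocol and SAP uses the same wording for these methods and for the correction.

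**The concern.** Randomisation protects the comparison of I with II, so an unadjusted rank test is a natural choice there. Nothing protects the comparison with Randers. Hospital, municipality, and the wards and staff through which patients are enrolled all differ.

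Frailty is the obvious confounder. The Conclusion of the Protocol's background states that the MPI predicts LOS. Frailty is also measured differently: controls are scored with a "frailty screening tool based exclusively on data collected through medical records", so the cohorts may differ in true frailty, in how it is scored, or both. The investigators foresee this, since they promise correction. Yet the three rank-tested outcomes are the ones whose named method cannot take a covariate, whereas the Cox and linear models can.

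What is at stake is that a difference in case mix between two hospitals could be reported as an effect of the care model on hospital stay. There is also an asymmetry in reporting. For readmission the plan promises hazard ratios with 95% confidence intervals. For LOS it promises medians and a test, with no estimate of the difference and no interval.

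**Working it through.** **1. The plan's own figures.** The Sample size section gives 758 per trial arm (readmission 13.7% v 8%, 90% power) and 1,019 (90-day mortality 20.6% v 15.6%, 80% power). A two-proportion formula with continuity correction and two-sided 5% level gives 659 and 970 per arm. Then 659 × 1.15 = 757.9, rounded up to 758, and 970 × 1.05 = 1,018.5, rounded up to 1,019. Both reproduce, but both concern I against II. The documents give no size for the Randers cohort, no LOS distribution by frailty and no share of severely frail patients. Everything below is therefore illustration.

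**2. Assumptions.** LOS is log-normal with SD of log 0.9. The severe:moderate ratio of median stay, r, is 1.25, 1.5 or 1.67 (5 days v 3 days). The share of severely frail patients differs between cohorts by d = 5, 10 or 15 percentage points. There are 758 per group and no true group effect.

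**3. Formulas.**

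- Probability that a severely frail patient stays longer than a moderately frail one: θ = Φ(ln r / (0.9√2)). For r = 1.25, 1.5 and 1.67 this is 0.570, 0.625 and 0.656.
- Shift in the rank-sum probability caused by case mix alone: d × (θ − 0.5).
- Null standard error: √(2/(12 × 758)) = 0.0148.
- Two-sided rejection rate with z = shift / SE: Φ(z − 1.96) + Φ(−z − 1.96).

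Worked case, r = 1.67 and d = 0.15: the shift is 0.15 × 0.156 = 0.0234, z = 1.58, and the test rejects 35.1% of the time.

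**4. Rejection rate of the nominal 5% rank-sum test, no true effect.**

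| LOS ratio | 5 points | 10 points | 15 points |
|---|---|---|---|
| 1.25 | 5.6% | 7.6% | 10.8% |
| 1.5 | 7.1% | 13.4% | 24.4% |
| 1.67 | 8.2% | 18.3% | 35.1% |

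With 300 per group, also an assumption, ratio 1.25 gives 5.2% to 7.3%.

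**5. Does adjustment remove it?** A simulation used log-SD 0.8, median stay 2 days in moderate frailty, stays rounded up to whole days, 758 per group and 1,000 runs per scenario. It compared the plain rank-sum test with a rank test stratified by frailty (van Elteren).

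| Severely frail | Rank-sum, ratio 1.25 / 1.5 | Stratified, ratio 1.25 / 1.5 |
|---|---|---|
| 40% v 40% | 3.5% / 4.5% | 3.8% / 4.0% |
| 45% v 40% | 6.2% / 8.4% | 6.0% / 5.3% |
| 50% v 40% | 8.8% / 18.1% | 5.3% / 5.1% |
| 55% v 40% | 13.1% / 27.5% | 5.6% / 5.7% |

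The stratified test stays near 5%. At 1,019 per group, ratio 1.5 and 55% v 40%, the rates are 36.5% and 4.2%. In the simulation frailty is measured without error and is the only confounder, so it shows adjustment at its best. No figures were worked out for time at home or duration of readmission.

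**The case against.** A reader might infer that the Randers comparison of LOS is bound to stay unadjusted even if an imbalance is found. The documents do not support that. The correction sentence follows directly on the three-group baseline comparison and is not limited to the Cox outcomes. It could be honoured by a stratified rank test, weighting, matching or an added regression. What stands is narrower: none of these is named, and an adjusted method chosen after the data are seen is what a prespecified plan should avoid.

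The rank-sum sentence also names no contrast. That it covers the Randers comparison is an inference from the second hypothesis, though a firm one, since no other method is given for these outcomes.

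The upper end of the range is not a prediction. It takes the strongest LOS ratio and the largest imbalance considered. Both cohorts are restricted to MPI levels 2 and 3, which narrows the frailty range without preventing imbalance. At the mild end the inflation is slight.

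Nor is a rank test incapable of giving an effect size. A Hodges–Lehmann estimate with an interval could accompany it, but the plan does not name one.

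Finally, calling the rank-sum test suitable for I against II presumes that the randomised groups are kept intact. Some listed exclusions concern events after the open allocation on the day of admission, such as transfer or discharge to one particular nursing home. That is a separate question.

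**Conclusion.** The concern holds as a gap in the named analysis. For LOS, time at home before readmission and duration of readmission against Randers, the only stated method takes no covariates, and the conditional promise of correction has no stated means of being carried out. This follows from the text and needs no assumed figure.

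The size does depend on assumptions. For LOS at 758 per group, ratios of 1.25 to 1.67 and imbalances of 5 to 15 points give false-positive rates of 5.6% to 35.1%; smaller groups give less. The LOS spread, the ratios, the frailty shares and the control-group size are all assumed.

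These are secondary outcomes in the cohort study. The primary outcome, mortality and the randomised comparison are untouched by this point. The change should be made because it is cheap and otherwise the LOS result against Randers would be hard to interpret.

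**What to change.** Keep the rank-sum test for intervention I against II. For each intervention against Randers, make the main LOS analysis covariate-adjusted:

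- **Covariates:** fix the list in advance and apply it whether or not imbalance is seen. MPI level, age, gender, number of drugs and co-habitation status are already planned as baseline data for all three groups. The list must be written out, because the plan gives none for the readmission model to borrow.
- **Model:** for example, median (quantile) regression, reporting an adjusted difference in median stay with 95% CI. Alternatively, regression for time to discharge alive with in-hospital death as a competing event, reporting a hazard ratio with 95% CI. Choose one and state its estimate, since the two are on different scales.
- **Other outcomes:** name an equivalent adjusted analysis for time at home before readmission and for duration of readmission.
- **Unadjusted results:** any rank-sum result against Randers should be labelled descriptive.

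The cost is about a paragraph in the SAP and a little more analysis work, with no new data. Adjustment will not remove everything. Exposure coincides with hospital, so local discharge practice remains confounded with the care model, and frailty in controls comes from a record-based tool. Both limits should be stated beside the results.

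### The day-30 comparison of function between I and II is made among survivors only, so a difference in 30-day mortality can distort it

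*Protocol*

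**What the plan says.** In the Protocol (February 2019), the Outcomes part of Statistical analyses gives one sentence on function: "The change in functional status at discharge and 30 days after discharge will be compared in a linear regression model". The Combined protocol and SAP (December 2018) has the same sentence. FRS at day 30 is listed only for the intervention cohort, so the comparison is I versus II. Functional recovery is a named measure in the first and third hypotheses.

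The Outcome measures section of both documents says: "Functional status is of relevance, especially combined with mortality data", and gives the reason: "since a better survival of the frailest may be combined with a worsened functional status in the total group".

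The analysis section treats mortality separately: "The mortality hazard ratio will be calculated also using the Cox regression model". For readmission, death enters as a competing risk. For function there is no value for patients who die, no composite or joint model, no statement that the comparison is among survivors, and no rule for missing scores. The statement on analysis sets, "Data will be analyzed in accordance with intention-to-treat and per-protocol analysis", does not say how a patient without a day-30 score enters the regression.

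**The concern.** The background names a specific hazard, and the analysis section does not act on it. A regression of FRS change can use only patients who are alive and scored at day 30. That group is formed after randomisation and may differ between the arms. If one arm keeps more very frail patients alive, they enter that arm's mean, while their counterparts in the other arm are absent.

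The plan itself considers a mortality difference: the Sample size section reports lower pilot mortality in II and gives a number per arm to detect it. The effect the sponsor hopes to see on mortality is therefore one under which the functional comparison can mislead. At stake is a secondary outcome on which two of the three hypotheses partly rest.

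**Working it through.** **The plan's own figures.** No sample size is given for function. The two stated sizes reproduce with a two-sided 5% test of two proportions with continuity correction:

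- Readmission, 13.7% v 8%, power 90%: 659 per arm; 659 × 1.15 = 758.
- 90-day mortality, 20.6% v 15.6%, power 80%: 970 per arm; 970 × 1.05 = 1,018.5, rounded up to 1,019.

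They are not in dispute.

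**Inputs from the Sample size section.** The readmission calculation is described as "allowing a 5% drop-out rate and a 30-day mortality rate of 10" per cent. Mortality at 30 days is not split by arm. At 10%, about 76 of 758 patients per arm (102 of 1,019) would have no day-30 score because of death. After 5% drop-out, 758 × 0.95 = 720 per arm.

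**Assumptions.** There is no true effect on function. The 10% applies to the period before the day-30 assessment. Everyone who would survive under I would also survive under II. The extra survivors in II have a mean FRS change d standard deviations below the other survivors. The documents give no value for d, so 0.5 to 1.5 is shown. The comparison is unadjusted.

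**Formulas**, with m for 30-day mortality:

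- share of extra survivors in II: f = (m_I − m_II) / (1 − m_II)
- bias = f × d
- SE = √(1/n_I + 1/n_II), in SD units, with n the survivors per arm
- false-positive rate = P(|Z + bias/SE| > 1.96)

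**Main case: pilot 90-day ratio applied to a 10% mean.** Ratio 15.6/20.6 = 0.757; m_I = 0.20/1.757 = 11.4%; m_II = 8.6%. Survivors are 638 and 658, about 20 of them extra. f = 0.0276/0.9138 = 0.0302; SE = 0.0556.

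**Extreme case: the full 5-point gap already present at day 30** (12.5% v 7.5%). Survivors are 630 and 666, 36 of them extra. f = 0.05/0.925 = 0.0541; SE = 0.0556.

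| Case | d (SD) | Bias (SD) | False-positive rate |
|---|---|---|---|
| 11.4% v 8.6% | 0.5 | 0.015 | 5.9% |
| 11.4% v 8.6% | 1.0 | 0.030 | 8.5% |
| 11.4% v 8.6% | 1.5 | 0.045 | 12.9% |
| 12.5% v 7.5% | 0.5 | 0.027 | 7.8% |
| 12.5% v 7.5% | 1.0 | 0.054 | 16.3% |
| 12.5% v 7.5% | 1.5 | 0.081 | 30.9% |
| equal mortality | any | 0 | 5.0% |

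With 1,019 per arm less 5%, the bias is the same but the SE falls to 0.048. The false-positive rate becomes 6.2% to 15.7% in the main case and 8.7% to 39.4% in the extreme case.

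**The same check on a ranked analysis with death as worst.** By simulation with 720 per arm, 12.5% v 7.5% mortality and no effect on function, the rank-sum test rejects in about 36%, 15% and 9% of trials for d = 0, 1 and 1.5. These rejections mostly favour II, because the test responds to survival.

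**The case against.** Four points can be made for the plan.

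- **Direction.** The outcome is change, not level. A patient already low at discharge has little room to fall, so the extra survivors may not show a worse change. This stands: the bias is possible, not certain, and its sign is not fixed.
- **Adjustment.** The plan allows correction for frailty where needed, and a regression can take covariates. Adjustment for the frailty index would absorb part of the bias. The provision is conditional, and it cannot correct for what the index does not capture, so it is a partial answer.
- **Visibility.** Mortality at 30 days after discharge is a secondary outcome at the same time point, so a survival difference would be reported. That helps a careful reader but leaves the functional estimate and its p-value as they are.
- **The alternative.** Ranking death as worst answers a different question and counts mortality again. The simulated rejection rates bear this out. It is a reason not to make the ranked test the main functional result, but not a reason to leave deaths out altogether.

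A reader might also take the rates of 16% and 31% as the expected error. The documents do not support that: those rates carry a 90-day gap, counted from admission, over to day 30, and the larger also needs d = 1.5 SD.

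**Conclusion.** The gap is real. As written, the functional comparison is among survivors, and the analysis section does not carry out the reading with mortality that the background calls for.

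The likely size is small to moderate: about 0.015 to 0.045 SD, with a false-positive rate of about 6% to 13%. This rests on the pilot ratio holding at day 30, an overall mortality of 10%, 720 per arm, and extra survivors 0.5 to 1.5 SD worse in change. A rate near 31% is an extreme case.

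A reader might infer that the arm that saves more lives will be penalised on function. The documents do not show this. It would need a mortality difference by day 30 and a worse change among the extra survivors, and neither is documented. The point merits a change to the plan, but concerns a secondary outcome and does not touch the primary analysis.

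**What to change.** In the Outcomes part of Statistical analyses:

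1. Keep the linear regression of FRS change, label it as a comparison among patients alive and assessed at day 30, and report it beside the number of deaths per arm.
2. Add a prespecified analysis of I versus II in randomised patients. Rank deaths before the day-30 assessment, including deaths before discharge, below the worst FRS, and rank survivors by day-30 FRS. Use the rank-sum test already planned for length of stay, and report the probability that a patient in II does better than one in I.
3. State the rule for living patients without a day-30 FRS.
4. State that a conclusion on functional recovery will be drawn only from both analyses read together.

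The cost is a few sentences and one more analysis. Death dates and day-30 FRS are already to be collected for both arms. The downside is that the ranked result mixes survival with function, and so must not be read as an effect on function alone. It also makes no use of the discharge score, which is a further reason to keep the regression.
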